5.4.1 Contraception

Women of childbearing potential must be willing to abstain from heterosexual activity or use an effective method of contraception from the time of informed consent until 5 months after the last dose of investigational product. Women of childbearing potential are defined as any female who has experienced menarche and who has not undergone surgical sterilization (hysterectomy or bilateral oophorectomy) or who is not postmenopausal. Menopause is defined clinically as 12 months of amenorrhea in a woman over 45 in the absence of other biological or physiological causes. In addition, women under the age of 62 must have a documented serum follicle stimulating hormone (FSH) level higher than 40 mIU/mL.

Men who are sexually active with WOCBP must use any contraceptive method with a failure rate of less than 1% per year. Men receiving study drug and who are sexually active with WOCBP will be instructed to adhere to contraception for a period of 7 months after the last dose of investigational product.

Subjects should be informed that taking the study medication may involve unknown risks to the fetus (unborn baby) if pregnancy were to occur during the study. To participate in the study, they must adhere to the contraception requirements described above for the duration of the study and during the follow-up period. If there is any question that a subject will not reliably comply with the requirements for contraception, that subject should not be entered into the study.

5.4.1.1 Highly Effective Methods of Contraception

- Male condoms with spermicide
- Hormonal methods of contraception including combined oral contraceptive pills, vaginal ring, injectables, implants and intrauterine devices (IUDs) such as Mirena[®] by WOCBP subject or male subject's WOCBP partner. Female partners of male subjects participating in the study may use hormone based contraceptives as one of the acceptable methods of contraception since they will not be receiving study drug
- Nonhormonal IUDs, such as ParaGard[®]
- Tubal ligation
- Vasectomy
- Complete Abstinence*

*Complete abstinence is defined as complete avoidance of heterosexual intercourse and is an acceptable form of contraception for all study drugs. Subjects who choose complete abstinence are not required to use a second method of contraception. Acceptable alternate methods of highly effective contraception must be discussed in the event that the subject chooses to forego complete abstinence.

5.4.1.2 Less Effective Methods of Contraception

- Diaphragm with spermicide
- Cervical cap with spermicide

- Vaginal sponge
 - Male Condom without spermicide
 - Progestin only pills by WOCBP subject or male subject's WOCBP partner
 - Female Condom*.
- * A male and female condom must not be used together

6. TOXICITIES AND DOSE DELAYS/DOSE MODIFICATIONS

The NCI Common Terminology Criteria for Adverse Events (CTCAE) v5 will be used to grade adverse events.

Subjects enrolled in this study will be evaluated clinically and with standard laboratory tests before and at regular intervals during their participation in this study as specified in Study Calendar & Evaluations.

Subjects will be evaluated for adverse events (all grades), serious adverse events, and adverse events requiring study drug interruption or discontinuation as specified in Study Calendar & Evaluations.

Please see section 17.1 for management of toxicities that may arise during the course of treatment.

6.1 Dose Delays/Dose Modifications

Guidelines for delaying, restarting, or discontinuing therapy for various toxicities is included in sections 17.1 and 17.2. Dose modifications are not permitted for this protocol, except if Day 1 weight change by >10% necessitates a change in the dosing of cabiralizumab. If therapy is delayed, then next infusion date will be considered day 1 of the subsequent cycle.

In addition to sections 17.1 and 17.2, please see below for dose delays related to hematologic toxicity:

- For Grade 1-2 (neutrophils <LLN to 1,000/ μ L, hemoglobin <LLN to 8 g/dL, platelets <LLN to 50,000/ μ L)
 - Rule out alternative causes
 - Continue cabiralizumab and nivolumab therapy
 - Monitor CBC per schedule of events
 - If worsens, treat as grade 3-4 toxicity
- For Grade 3-4 (neutrophils < 1,000/ μ L, hemoglobin < 8 g/dL, platelets < 50,000/ μ L)
 - Rule out alternative causes
 - Delay cabiralizumab and nivolumab therapy. If the AE requiring dose delay was due to one of the study drugs, the non-offending drug may be continued, taking into account the safety and clinical benefit to the patient.
 - Treat autoimmune cytopenias per standard institutional guidelines (examples below):
 - Immune thrombocytopenia may be treated with steroids, immune globulin, or rituximab
 - Immune mediated hemolytic anemia may be treated with steroids, immune globulin, or rituximab
 - Immune mediated neutropenia may be treated with steroids, colony stimulating factors, or immune globulin
 - If improves to < grade 3:

- May resume cabiralizumab and nivolumab therapy per protocol
- If does not improve or worsens:
 - Discontinue therapy. If the AE requiring discontinuation was due to one of the study drugs, the non-offending drug may be continued, if there is timely resolution of AE and clinical benefit is shown by patient.
 - Continue to treat immune mediated cytopenias per standard algorithms
 - Continue follow up until resolution
- Grade 3 drug-related thrombocytopenia associated with grade ≥ 2 bleeding requires discontinuation regardless of duration of thrombocytopenia.

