6.3 Protocol Therapy Discontinuation

The reason for discontinuation of protocol therapy will be documented on the electronic case report form (eCRF).

Instructions for management and discontinuation of therapy for common or expected AEs is included in sections 17.1 and 17.2. Please refer to these sections for instructions regarding therapy discontinuation for diarrhea/colitis, hepatic toxicity, renal toxicity, pulmonary toxicity, endocrinopathy toxicity, skin toxicity, neurologic toxicity, periorbital edema, uveitis, and CK or LDH elevation. In addition, criteria for discontinuation due to hematologic toxicity are outlined in section 6.1. In addition to these, a subject will also be discontinued from protocol therapy and followed up per protocol under the circumstances outlined below.

- Documented disease progression
- The treating physician thinks a change of therapy would be in the best interest of the subject
- The subject requests to discontinue protocol therapy, whether due to unacceptable toxicity or for other reasons
 - If a subject decides to prematurely discontinue protocol therapy (“refuses treatment”), the subject should be asked if he or she may still be contacted for further scheduled study assessments. The outcome of that discussion should be documented in both the medical records and in the eCRF.
- A female subject becomes pregnant
- Any Grade 3 or higher infusion-related reactions and hypersensitivity requiring discontinuation. Any re-initiation of therapy in this circumstance would require consultation with the Sponsor’s Medical Monitor or designee.
- Isolated Grade 3 electrolyte imbalances/abnormalities that are not associated with clinical sequelae
- Any Grade 4 drug-related AE or laboratory abnormality not addressed in sections 6.1, 17.1, or 17.2, except for the following events which do not require discontinuation:
 - Refractory hematologic toxicities as in section 6.1
 - Isolated Grade 4 amylase or lipase abnormalities that are not associated with symptoms or clinical manifestations of pancreatitis. The Sponsor’s Medical Monitor or designee should be consulted for Grade 4 amylase or lipase abnormalities.
 - Isolated Grade 4 electrolyte imbalances/abnormalities that are not associated with clinical sequelae and are corrected with supplementation/appropriate management within 72 hours of their onset

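### Section 6.1's mandatory bleeding stop names Grade 3 thrombocytopenia but not Grade 4, so in one narrow case the more severe event gets the less strict instruction

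*Combined protocol and SAP*

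**What the plan says.** Section 6.1 puts Grade 3 and Grade 4 cytopenias (platelets below 50,000/µL) on one pathway. Both drugs are delayed. If the count improves to below Grade 3, the instruction is "May resume cabiralizumab and nivolumab therapy per protocol", with no condition about bleeding. The other branch, "If does not improve or worsens", leads to discontinuation. A separate last bullet, beginning "Grade 3 drug-related thrombocytopenia associated with grade", makes bleeding of grade 2 or higher a mandatory stop however long the thrombocytopenia lasts.

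Section 6.3 adds a general Grade 4 stop, limited to "Any Grade 4 drug-related AE or laboratory abnormality not addressed in sections 6.1, 17.1, or 17.2". Among the exceptions to it, listed as not requiring discontinuation, is "Refractory hematologic toxicities as in section 6.1". The opening paragraph of 6.3 says that "criteria for discontinuation due to hematologic toxicity are outlined in section 6.1". Section 6.3 also has two stops that rest on judgement. One is "The treating physician thinks a change of therapy would be in the best interest of the subject"; the other is the investigator's opinion that continued dosing carries substantial clinical risk.

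Section 12.3 uses these provisions in its second interim safety rule (rule 2). Enrollment stops if at least 3 of the first 17 subjects have Grade 4 AEs that require discontinuation as specified in 6.3. Rule 1 stops enrollment if at least 7 of 17 have any Grade 4 AE.

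**The concern.** A mandatory safety stop should not become discretionary as the toxicity gets worse. The bullet in 6.1 uses a greater-than-or-equal sign for the bleeding grade but none for the platelet grade, so Grade 4 falls outside its words. The place where one would expect Grade 4 to be picked up, the general stop in 6.3, excludes whatever 6.1 already addresses. Sections 17.1 and 17.2 contain no platelet or bleeding rule.

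Two things are at stake. First, a subject who has had drug-related bleeding at a Grade 4 platelet count can be re-dosed where a Grade 3 subject could not, and sites in a multicenter trial may apply the text differently. Second, a subject who was not required to stop is not counted in rule 2, where the threshold is only three. The 6.3 exemption for refractory hematologic events adds a related difficulty: taken alone, it says the opposite of 6.1 and invites argument over that count.

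**Working it through.** **1. The plan's own figures.** I enumerated the 17 + 16 design exactly, with CR nested within OR and toxicity independent of response. The inputs from 12.3 are: futility if CR < 3 and OR < 7 of 17; success if CR ≥ 7 or OR ≥ 17 of 33; Grade 4+ AE rate 32%.

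- Rule 1: P(X ≥ 7 | n = 17, p = 0.32) = 0.2838.
- CRR 30%, ORR 30%: success on efficacy alone is 0.8674, so success = 0.8674 × (1 − 0.2838) = 0.621. Futility probability is 0.0774, so interim stop = 1 − (1 − 0.0774)(1 − 0.2838) = 0.339.
- CRR 10%, ORR 30%: success = 0.0418 × (1 − 0.2838) = 0.030. Futility probability is 0.6492, so interim stop = 1 − (1 − 0.6492)(1 − 0.2838) = 0.749.

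These match the stated 0.62, 0.34, below 0.05 and about 0.75. They use futility and rule 1 only, so a gap in what rule 2 counts does not make them wrong.

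**2. Which cases the text already covers.** Each combination of drug-related thrombocytopenia and bleeding is set against 6.1 and 6.3.

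- Count at Grade 3 with bleeding of grade 2 or higher: the last bullet of 6.1 applies. Mandatory stop.
- Held Grade 3 count that falls to Grade 4: this has worsened under 6.1. Mandatory stop.
- Grade 4 count that does not improve: the same branch of 6.1. Mandatory stop.
- Drug-related Grade 4 bleeding: the bleeding itself falls under the general Grade 4 stop in 6.3. Mandatory stop.
- Count first found at Grade 4, with bleeding still at grade 2 or higher as the count rises through the Grade 3 range: the last bullet applies at that moment, whatever the duration. Mandatory stop.
- Count first found at Grade 4, with drug-related Grade 2-3 bleeding that settles below grade 2 while the count is still Grade 4, then recovery below Grade 3: no mandatory grade-based stop applies. Both drugs may resume, subject to judgement under 6.3.

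Only the last case is open. First detection at Grade 4 is plausible, because the study calendar in section 7 schedules the CBC on Day 1 of each 14-day cycle.

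**3. Possible effect on rule 2.** The documents give no rate for events counted under rule 2 or for the open case, so the figures below are assumptions. Rule 2 events are nested in the 32% Grade 4+ rate, and power is taken at CRR 30%, ORR 30%, where it is lowest. P(rule 2 stops) = P(X ≥ 3 | n = 17, p).

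If the fix adds 1 percentage point to the counted rate:

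- 3% already counted: rule 2 stops with probability 2.9% instead of 1.3%; power 0.612 instead of 0.617.
- 5% already counted: 7.8% instead of 5.0%; power 0.595 instead of 0.605.
- 10% already counted: 28.6% instead of 23.8%; power 0.504 instead of 0.527.

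One point is probably high for so narrow a case. If the fix adds 0.1 to 0.25 points, power falls by about 0.0004 to 0.0055 over the same three base rates.

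**4. The 6.3 exemption.** It sits under a stop that already leaves out events addressed in 6.1, it refers to 6.1 itself, and 6.3 opens by sending the reader to 6.1 for hematologic criteria. The likely reading is therefore that 6.1 governs and refractory Grade 4 cytopenias both require discontinuation and count in rule 2. The exemption's literal words say that they do not require discontinuation.

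**The case against.** The strongest reply is that the gap is very small and that judgement closes it. Resumption is a permission, and it needs platelets of at least 50,000/µL. A recovering count has to pass through Grade 3, where persistent grade 2 or higher bleeding triggers the stop. Section 6.3 also requires discontinuation when the investigator sees substantial clinical risk. All of this stands, and it rules out one tempting inference: that the text lets a subject be re-dosed while still bleeding at grade 2 or higher. It does not. What the reply leaves standing is that the Grade 3 subject's stop is mandatory and the Grade 4 subject's is discretionary, and nothing in the text justifies that order.

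A reader might also infer that the protocol treats Grade 4 as a permanent stop everywhere else, since 17.1.1 does so for diarrhea and colitis while letting Grade 3 resume. The documents do not support that as a general principle. Section 17.1.7 lets Grade 3-4 rash resume after improvement, and 6.3 exempts certain Grade 4 laboratory and endocrine events. The point rests on the ordering within 6.1 alone.

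On the 6.3 exemption, the reply is largely right. The exemption only carves out of a stop that already leaves out 6.1 events, so it cannot repeal 6.1. What remains is a wording conflict in the section that rule 2 cites.

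**Conclusion.** Wrong as written: a mandatory safety stop is less strict for the more severe event. The defect is confined to a count first found at Grade 4 with drug-related Grade 2-3 bleeding that settles below grade 2 before the count re-enters the Grade 3 range, followed by recovery. Its frequency cannot be estimated from the documents and is likely low. The power figures above are illustrations under assumed rates.

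The 6.3 exemption is a supporting clarification. A reader might infer that refractory Grade 4 cytopenias go uncounted in rule 2, or that the stated operating characteristics fail. Neither follows. Section 6.1 most likely governs, the stated 0.62, 0.34 and about 0.75 reproduce with rule 1 alone, and a Grade 4 event recorded as an AE still counts toward rule 1.

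**What to change.** - Section 6.1, last bullet: change the platelet grade from 3 to ≥3 and leave the rest of the sentence as it is.
- Section 6.3: replace the exemption for refractory hematologic toxicities with *Grade 4 hematologic toxicities that improve to < Grade 3 as in section 6.1, other than thrombocytopenia with grade ≥2 bleeding*. This brings 6.3 into line with 6.1 and settles which hematologic events count in rule 2.

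Section 12.3 need not change, because 6.3 already points to 6.1, 17.1 and 17.2 for discontinuation criteria.

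The cost is two wording changes, with no new data, visits or sample size. A rare subject whose platelets recover would have to stop therapy. Rule 2 could trip slightly more often, with a small loss of power whose size the documents do not allow one to state.

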6.2 Cabiralizumab and Nivolumab-Related Infusion Reactions

Cabiralizumab and nivolumab may induce infusion or hypersensitivity reactions. If such reactions occur, they may manifest with fever, chills, rigors, headache, rash, pruritus, arthralgia, hypotension or hypertension, bronchospasm, or other symptoms.

Infusion reactions should be graded according to CTCAE v5 guidelines. Any Grade 3 or Grade 4 infusion reaction should be reported to Big Ten CRC AHQ within 24 hours and reported as an SAE if it meets the criteria.

The nivolumab 30-minute infusion will be administered first, with a 30-minute rest, followed by the cabiralizumab 30-minute infusion. It may be unclear if an infusion reaction is due to cabiralizumab, nivolumab, or to both study drugs. Therefore, one set of treatment recommendations (based on the most conservative treatments for infusion reactions due to either study drug) is provided below and may be modified based on clinical judgment, local treatment standards and guidelines, and/or specific symptoms, as appropriate.

For Grade 1 symptoms: Mild reaction (eg, localized cutaneous reactions including mild pruritus, flushing, and rash), requires infusion rate to be decreased; intervention may be indicated.

- Decrease the rate of the study drug infusion until recovery from symptoms.
- Remain at bedside and monitor the patient's vital signs until resolution of symptoms.
- Diphenhydramine 50 mg may be administered at the discretion of the treating physician.
- When symptoms resolve, restart the infusion at the original infusion rate.
- If a patient has an infusion reaction with nivolumab, cabiralizumab can be given (without prophylactic medications) if the infusion reaction resolves within 3 hours. For scheduling purposes, the cabiralizumab infusion may be given the next day. Prophylactic pre-infusion medications should be given prior to all subsequent nivolumab infusions.
- If a patient has an infusion reaction with cabiralizumab, prophylactic pre-infusion medications should be given prior to all subsequent cabiralizumab and nivolumab infusions.
- The following prophylactic pre-infusion medications are recommended prior to future infusions of cabiralizumab and nivolumab: diphenhydramine 50 mg (or equivalent) and/or paracetamol (acetaminophen) 325 mg to 1000 mg at least 30 minutes before additional study drug administrations.

For Grade 2 symptoms: Moderate reaction (ie, any symptom not listed above [mild symptoms] or below [severe symptoms] such as generalized pruritus, flushing, rash, dyspnea, and hypotension with systolic blood pressure >80 mmHg), requires infusion interruption but responds promptly to

symptomatic treatment (eg, antihistamines, nonsteroidal anti-inflammatory drugs, narcotics, corticosteroids, and IV fluids); prophylactic pre-infusion medications indicated for ≥ 24 hours.

- Interrupt the study drug infusion.
- Begin an IV infusion of normal saline and treat the patient with diphenhydramine 50 mg IV (or equivalent) and/or paracetamol (acetaminophen) 325 mg to 1000 mg.
- Remain at bedside and monitor the patient's vital signs until resolution of symptoms.
- Corticosteroid therapy may be administered at the discretion of the treating physician.
- When symptoms resolve, restart the infusion at 50% of the original infusion rate; if no further complications ensue after 30 minutes, the rate may be increased to 100% of the original infusion rate.
- Monitor the patient closely. If symptoms recur, immediately discontinue the infusion; no further study drug will be administered at that visit. Administer diphenhydramine 50 mg IV, and remain at bedside and monitor the patient until resolution of symptoms.
- If a patient has an infusion reaction with nivolumab infusion, cabiralizumab infusion can be given (without prophylactic medications) if the infusion reaction resolves within 3 hours. For scheduling purposes, the cabiralizumab infusion may be given the next day. Prophylactic pre-infusion medications should be given prior to all subsequent nivolumab infusions.
- If a patient has an infusion reaction with cabiralizumab, prophylactic pre-infusion medications should be given prior to all subsequent cabiralizumab and nivolumab infusions.
- The following prophylactic pre-infusion medications are recommended prior to future infusions of cabiralizumab and nivolumab: diphenhydramine 50 mg (or equivalent) and/or paracetamol (acetaminophen) 325 mg to 1000 mg should be administered at least 30 minutes before additional study drug administrations. If necessary, corticosteroids (up to 25 mg of SoluCortef or equivalent) may be used.
- The amount of study drug infused must be recorded.

For Grade 3 or Grade 4 symptoms: Severe reaction such as bronchospasm, generalized urticaria, systolic blood pressure < 80 mmHg, or angioedema; Grade 3 symptoms including prolonged symptoms, which require 6 or more hours to respond to symptomatic medication and/or discontinuation of infusion; recurrence of symptoms following initial improvement; hospitalization indicated for other clinical sequelae, such as renal impairment, pulmonary infiltrates; Grade 4: life-threatening; pressor or ventilation support indicated.

- Immediately discontinue the study drug infusion. No further study drug will be administered. The amount of study drug infused must be recorded on the CRF.
- Begin an IV infusion of normal saline and treat the patient as follows: Recommend bronchodilators, epinephrine 0.2 mg to 1.0 mg of a 1:1,000 solution for subcutaneous administration or 0.1 mg to 0.25 mg of a 1:10,000 solution injected slowly for IV administration, and/or diphenhydramine 50 mg IV with methylprednisolone 100 mg IV (or equivalent), as needed.
- Remain at bedside and monitor the patient's vital signs until recovery from symptoms.
- The patient should be monitored until the investigator is comfortable that the symptoms will not recur.
- Investigators should follow their institutional guidelines for the treatment of anaphylaxis.

In the case of late-occurring hypersensitivity symptoms (eg, appearance of a localized or generalized pruritus within 1 week after treatment), symptomatic treatment may be given (eg, oral antihistamine or corticosteroids).

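### Section 6.2 limits the stop after a recurrent Grade 2 infusion reaction to one visit, although the same section describes such a recurrence as Grade 3

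*Combined protocol and SAP*

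**What the plan says.** Section 6.2 gives one set of management steps for infusion reactions to either drug, arranged by grade.

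- **Grade 2.** The block covers "any symptom not listed above [mild symptoms] or below [severe symptoms"], reactions that need interruption but respond promptly to treatment. Once symptoms resolve, the infusion restarts at half rate. The next step reads: "If symptoms recur, immediately discontinue the infusion; no further study drug will be administered at that visit".
- **Later bullets in the same block.** If nivolumab caused the reaction and it resolves within 3 hours, cabiralizumab can still be given: "For scheduling purposes, the cabiralizumab infusion may be given the next day". They add: "Prophylactic pre-infusion medications should be given prior to all subsequent nivolumab infusions".
- **Grade 3 or 4.** The Grade 3 features include "recurrence of symptoms following initial improvement". The action is to stop the infusion, followed by "No further study drug will be administered".
- **Reporting.** "Any Grade 3 or Grade 4 infusion reaction should be reported to Big Ten CRC AHQ within 24 hours".

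Section 6.3 lists Grade 3 or higher infusion reactions that require discontinuation among the reasons to stop protocol therapy. In that circumstance, re-initiation requires consultation with the Sponsor's Medical Monitor or designee.

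**The concern.** The Grade 2 recurrence step can apply only after symptoms have resolved and the infusion has been restarted. That sequence is what the Grade 3 text describes, yet the step stops drug for one visit and the Grade 3 text stops it without a time limit. A coordinator or infusion nurse working down the Grade 2 bullets would find nothing that sends them to the Grade 3 block.

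At stake is whether a subject whose hypersensitivity reaction returned on rechallenge is dosed again without the consultation that section 6.3 attaches to a Grade 3 reaction requiring discontinuation. Handling could also differ between sites in a multicenter trial.

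**Working it through.** There is no figure in the plan to reproduce. The check is a comparison of the text, with one calculation of timing.

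1. **The event.** A Grade 2 reaction occurs, the infusion is interrupted, symptoms resolve, the infusion restarts at half rate, and symptoms return.

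2. **Does it meet the Grade 2 recurrence step?** Yes. That step directly follows the half-rate restart and is written for this event.

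3. **Does it meet the Grade 3 description?** Yes. Symptoms that resolved have improved, and their return is a recurrence. The Grade 3 wording sets no condition on the grade of the first reaction.

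4. **What follows under each text?**

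| | Grade 2 recurrence step | Grade 3 text |
|---|---|---|
| Study drug | Withheld at that visit | Withheld, no visit limit |
| 24-hour report | Not triggered by this step; depends on the grade assigned | Required |
| Re-initiation | No consultation mentioned | Medical Monitor consultation under 6.3, where the reaction requires discontinuation |

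5. **How soon could dosing resume on the visit-limited wording?** Cabiralizumab could follow the next day after a nivolumab reaction that meets the 3-hour condition, because the next day can be read as outside that visit. Otherwise both drugs could be given at the next cycle. Section 5 sets a 14-day cycle and section 5.2 a window of 3 days either side: 14 − 3 = 11 days to 14 + 3 = 17 days.

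6. **Does any text rank the two blocks?** No sentence in sections 5.4, 6.2 or 6.3 does so. The remark in 6.2 about using the most conservative treatments explains why guidance for the two drugs was merged. Elsewhere the protocol makes escalation explicit: worsening haematologic toxicity in 6.1, and worsening or steroid-refractory diarrhoea in 17.1.1, are each redirected to the higher-grade instructions. The Grade 2 recurrence step has no such link.

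7. **Is there a statistical effect?** The interim safety rules in section 12.3 count Grade 4 events (at least 7 subjects), Grade 4 events requiring discontinuation (at least 3) and Grade 5 events attributable to drug. Moving an event between Grade 2 and Grade 3 changes none of these counts, and the response definitions in section 9.3 do not refer to infusion reactions.

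**The case against.** The strongest reply is that the protocol already answers the question. Grade 2 is defined to exclude symptoms listed as severe, and recurrence is on the severe list, so a recurrence leaves Grade 2 by definition. The recurrence step can then be read as the immediate bedside action, with the Grade 3 text governing what comes next. A site that gives no more drug breaches nothing in the Grade 2 block. The premedication and next-day bullets are written for Grade 2 reactions in general and do not expressly permit dosing after a recurrence. Grading by CTCAE v5 is required for every reaction, and the 24-hour report follows the grade whichever bullets were used. Finally, 6.2 allows its recommendations to be modified by clinical judgment.

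Most of this stands. A reader might infer that the two blocks are irreconcilable. They are not, because both can be obeyed by following the stricter one, and the text favours it. The objection does not remove the visit limit. If Grade 3 always governs, the words confining the stop to that visit have no work to do, and a site acting on them is following a sentence written for its case. The clinical-judgment clause neither ranks the blocks nor replaces the consultation in 6.3.

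A reader might also infer a separate gap for Grade 1, where the instruction is "When symptoms resolve, restart the infusion at the original infusion rate" and no recurrence step follows. The documents do not support treating that as a second defect: the Grade 3 wording, read literally, already covers recurrence after a Grade 1 restart, and no Grade 1 sentence points the other way. What is missing there is detail.

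**Conclusion.** The point holds as a minor defect in wording with a safety consequence. As written, the Grade 2 recurrence step lets a site resume dosing, without Medical Monitor consultation, in a subject whose reaction meets the protocol's own Grade 3 description. The conclusion rests on reading resolution followed by return of symptoms as recurrence after improvement, which is the plain sense of the words.

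The event should be rare, but its frequency is not estimable from the documents. Section 10.1.6 reports one infusion reaction and one hypersensitivity reaction with the combination. A reader might divide these by the 265 subjects at the recommended dose in section 1.6.2 (2/265 = 0.75%) and scale to this trial (0.0075 × 33 = 0.25 subjects with any reaction). That does not give the number affected: the two sections may not share a data cut-off, no grades are given, and the documents do not say what share of reactions recur after restart.

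Nor should a reader infer any harm to the trial's inference. Efficacy endpoints, interim Grade 4 and 5 thresholds and operating characteristics do not depend on this step.

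**What to change.** Replace the Grade 2 recurrence sentence in section 6.2 with wording to this effect:

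*If symptoms recur after restart, stop the infusion at once and treat the event as Grade 3: report it within 24 hours, and give no more study drug (including cabiralizumab under the 3-hour or next-day allowance) unless re-initiation is agreed after consultation with the Sponsor's Medical Monitor or designee per section 6.3.*

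The existing instructions on diphenhydramine and bedside monitoring stay as they are.

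The cost is one sentence at the next amendment, with no new procedures or data collection. The downside is that, for the rare subject affected, treatment stops by default until the consultation has taken place. Re-initiation remains possible through section 6.3.
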